5.2 Exclusion Criteria

- 1. Within 3 months of Screening: acute coronary syndrome, major cardiac surgery, or stroke/transient ischemic attack
- 2. Within 3 months of Screening: coronary, carotid, or peripheral arterial revascularization, major non-cardiac surgery, or lipoprotein apheresis
- 3. Heart failure NYHA class III and IV
- 4. Uncontrolled hypertension (systolic > 160 or diastolic > 100 mm Hg)
- 5. History of acute kidney injury within 12 months of Screening
- 6. Uncontrolled hyper or hypothyroidism
- 7. Active infection requiring systemic antiviral or antimicrobial therapy that will not be completed prior to Study Day 1
- 8. Known history of or positive test for human immunodeficiency virus (HIV), hepatitis C or chronic hepatitis B
- 9. Malignancy within 5 years, except for basal or squamous cell carcinoma of the skin or carcinoma *in situ* of the cervix that has been successfully treated
- 10. Patients at high-risk of bleeding diathesis
- 11. Recent history of, or current drug or alcohol abuse
- 12. Hypersensitivity to the active substance or to any of the excipients
- 13. Clinically-significant abnormalities in screening laboratory values that would render a patient unsuitable for inclusion, including the following:
 - a. Positive test (including trace) for blood on urinalysis. In the event of a positive test, eligibility may be confirmed with urine microscopy showing ≤ 5 red blood cells per high power field
 - b. Urine protein/creatinine ratio (UPCR) ≥ 0.25 mg/mg.

- c. Estimated GFR < 60 mL/min/1.73 m² (as determined by the Chronic Kidney Disease-Epidemiological Collaboration (CKD-EPI) Equation)
- d. Alanine aminotransferase (ALT) or aspartate aminotransferase (AST) > 2 x ULN
- e. Bilirubin > 1.2 x ULN, unless prior diagnosis and documentation of Gilbert's syndrome in which case total bilirubin must be \leq 3 mg/dL
- f. Alkaline phosphatase (ALP) > 1.5 x ULN
- g. Platelet count < LLN
- h. LDL-C > 130 mg/dL (> 3.4 mmol/L)

14. Type 1 diabetes mellitus

15. Type 2 diabetes mellitus with any of the following:

- a. Newly diagnosed within 12 weeks of Screening
- b. HbA1c \geq 9.0% at Screening
- c. Recent change in anti-diabetic pharmacotherapy (change in dosage or addition of new medication within 12 weeks of Screening [with the exception of \pm 10 units of insulin])
- d. Anticipated need to change dose or type of medication during the treatment period of the Study (with the exception of \pm 10 units for insulin)
- e. Current use of GLP-1 agonists, if patient has history of pancreatitis

16. Use of warfarin or other vitamin K antagonists, direct thrombin inhibitors or factor Xa inhibitors

17. Treatment with another investigational drug, biological agent, or device within 1 month of Screening, or 5 half-lives of investigational agent, whichever is longer

18. Treatment with any non-Akcea/non-Ionis oligonucleotide (including small interfering ribonucleic acid [siRNA]) at any time or prior treatment with an Ionis oligonucleotide or siRNA within 9 months of Screening. Patients that have previously received only 1 dose of an Ionis oligonucleotide as part of a clinical study may be included as long as \geq 4 months has elapsed since dosing

19. BMI > 40 kg/m²

20. Blood donation of 50-499 mL within 30 days of Screening or of > 499 mL within 8 weeks of Screening

21. Unwillingness to comply with study procedures, including follow-up, as specified by this protocol, or unwillingness to cooperate fully with the Investigator

22. Have any other conditions, which, in the opinion of the Investigator or Sponsor would make the patient unsuitable for inclusion, or could interfere with the patient participating in or completing the Study

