4. Serology for viral hepatitis (hepatitis A virus [HAV] immunoglobulin M [IgM], hepatitis B surface antigen [HBsAg], hepatitis C virus [HCV] antibody, Cytomegalovirus [CMV] IgM, and EBV antibody panel)
5. Serology for autoimmune hepatitis (e.g., antinuclear antibody [ANA])

Additional liver evaluations, including gastroenterology/hepatology consultations, hepatic CT or MRI scans, may be performed at the discretion of the Investigator, in consultation with the Sponsor Medical Monitor and the study DSMB. Repetition of the above evaluations should be considered if a patient's ALT and/or AST levels reach $5 \times \text{ULN}$.

All routine liver function test results will be reviewed on an ongoing basis at the weekly safety review by the Medical Monitor.

All lab alerts for abnormal liver function tests must be promptly reviewed by the Investigator (within 48 hours of receipt) and Medical Monitors (within 24 hours of receipt).

Lab alerts for abnormal liver chemistry tests will be issued for: 1) ALT or AST $> 3 \times \text{ULN}$; 2) ALT or AST $> 2 \times \text{baseline}$; 3) total bilirubin $> \text{ULN}$; 4) ALP $> \text{ULN}$. These alert levels are set to anticipate the risk of a combined elevation of aminotransferases and bilirubin as per the FDA Guidance referenced in [Section 8.5.1](#).

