8.6 Stopping Rules

Monitoring rules are described above in [Section 8.5](#).

For the purposes of stopping rules, Baseline is defined as the average of Day 1 pre-dose assessment and the last measurement prior to Day 1.

8.6.1 *Stopping Rules for Liver Chemistry Elevations*

In the event of confirmed laboratory results meeting any of the following criteria, dosing of a patient with Study Drug will be stopped permanently:

1. ALT or AST > 8 x ULN, which is confirmed
2. ALT or AST > 5 x ULN, which is confirmed and persists for \geq 2 weeks
3. ALT or AST > 3 x ULN (or the greater of 2 x Baseline value or 3 x ULN if the Baseline value was $>$ ULN), which is confirmed and total bilirubin $>$ 2 x ULN or INR $>$ 1.5
4. ALT or AST > 3 x ULN (or the greater of 2 x Baseline value or 3 x ULN if the Baseline value was $>$ ULN), which is confirmed, and the new appearance (i.e., onset coincides

with the changes in hepatic enzymes) of fatigue, nausea, vomiting, right upper quadrant pain or tenderness, fever, rash, or eosinophilia ($>$ ULN) felt by the Investigator to be potentially related to hepatic inflammation

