The number and percent of patients who stopped treatment because they met a protocol-defined safety monitoring rule(s) and stopping rule(s) (see Protocol Section 8.6 for details) will be tabulated by treatment group. A listing will be provided for patients who met protocol-defined safety monitoring rules and for patients who terminated treatment due to a protocol-defined stopping rule as well.

Additional investigation of abnormalities in liver chemistry, platelet counts, and renal functions will be performed for on-treatment and on-study periods as below.

Abnormalities in liver chemistry: The number and percent of patients falling in each of the following categories (using available central and local laboratory assessments) will be tabulated based on worst post-baseline assessments by treatment group and for pooled ISIS 678354.

- The higher of ALT > 3 x upper limit of normality (ULN) or ALT > 2 x Baseline
- ALT/AST > 3 x ULN
- ALT/AST > 5 x ULN
- ALT/AST > 8 x ULN
- ALT > 3 x ULN - ≤ 5 x ULN
- ALT > 5 x ULN - ≤ 8 x ULN
- Total bilirubin > 2 x ULN
- ALP > 2 x ULN and (baseline ALP < 2 x ULN or baseline ALP missing)

The number and percent of patients falling in each of the following categories based on confirmed worst post-baseline assessments will be tabulated by treatment group and for pooled ISIS 678354.

- ALT/AST > 8 x ULN, which is confirmed
- ALT/AST > 5 x ULN, which is confirmed and persist for at least 2 weeks
- ALT/AST > 3 x ULN (or the greater of 2 x Baseline value or 3 x ULN if the Baseline value was > ULN), which is confirmed and either:
 - Total bilirubin > 2 x ULN, or
 - INR > 1.5, or
 - Temporal association with symptoms of fatigue, nausea, vomiting, right upper quadrant pain or tenderness (PT: abdominal pain or abdominal pain upper), fever, rash, or eosinophilia (PT: Eosinophilia and the corresponding lab value >ULN within the interval of associated Eosinophilia start and end date); and where temporal will be defined as the report date of the confirmed laboratory parameter occurring within the interval of the associated adverse event start and stop dates

For patients having confirmed 3-fold or greater elevations above the ULN for ALT or AST, a listing of all ALT, AST, total bilirubin, INR, and alkaline phosphatase records will be provided.

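### Criterion 13e can admit a Gilbert's patient already above the 2 x ULN bilirubin limit used in liver stopping rule 3 and SAP 3.7.4, and neither place has a baseline term for bilirubin

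*Combined protocol and SAP*

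**What the plan says.** Criterion 13e (protocol section 5.2, repeated in the synopsis) excludes "Bilirubin > 1.2 x ULN, unless prior diagnosis and documentation of Gilbert's syndrome in which case total bilirubin must be" at most 3 mg/dL. That limit is absolute and not tied to the laboratory's ULN. Gilbert's syndrome is mentioned nowhere else in the protocol or SAP.

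Criterion 3 of section 8.6.1 stops dosing permanently for ALT or AST above 3 x ULN, "which is confirmed and total bilirubin $>$ 2 x ULN or INR $>$ 1.5". Within that criterion the aminotransferase part has a baseline provision ("or the greater of 2 x Baseline value or 3 x ULN if the Baseline value was" above ULN). The bilirubin part has none.

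SAP 3.7.4 lists liver abnormalities that "will be tabulated based on worst post-baseline assessments by treatment group and for pooled ISIS 678354". One row is "Total bilirubin > 2 x ULN", without a condition. The next row does carry a baseline condition: "ALP > 2 x ULN and (baseline ALP < 2 x ULN or baseline ALP missing". A second list, on confirmed values, repeats the combined stopping criterion, again with no baseline term for bilirubin.

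The number of patients meeting liver stopping rules is a named safety endpoint (protocol section 10.1.3, SAP 1.4.4).

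**The concern.** Eligibility knowingly admits a stable, pre-existing bilirubin elevation, and the later rules do not recognise it. Two things follow.

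- **Conduct.** A two-part rule is meant to need evidence from both parts. For a patient who starts above 2 x ULN, the bilirubin part carries no information about the drug, so a confirmed aminotransferase rise above 3 x ULN is enough for permanent discontinuation. Without the bilirubin, an INR above 1.5 or attributed symptoms, section 8.6.1 requires more than 8 x ULN, or more than 5 x ULN persisting for at least 2 weeks.
- **Reporting.** An unchanged Gilbert's value would be counted as a post-baseline liver abnormality. With an aminotransferase rise it would enter the combined row, the most serious liver category in the table. Within either row it cannot be told apart from a new elevation.

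**Working it through.** There is no stated figure to reproduce. The check compares thresholds.

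**Inputs.** Entry limit without Gilbert's syndrome: 1.2 x ULN. Entry limit with documented Gilbert's syndrome: 3 mg/dL (both criterion 13e). Bilirubin threshold: 2 x ULN (section 8.6.1 criterion 3 and SAP 3.7.4). Entry limits for ALT/AST and ALP: 2 x ULN and 1.5 x ULN (criteria 13d and 13f). The bilirubin ULN is not given, so it is varied as an assumption.

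**Step 1: can a permitted entry value exceed the threshold?** The condition is 3 > 2 x ULN, that is, ULN < 3 / 2 = 1.5 mg/dL.

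| Assumed ULN (mg/dL) | 2 x ULN (mg/dL) | 3 mg/dL as multiple of ULN | Permitted band above 2 x ULN (mg/dL) |
|---|---|---|---|
| 1.0 | 2.0 | 3.0 | 1.0 |
| 1.2 | 2.4 | 2.5 | 0.6 |
| 1.4 | 2.8 | 2.1 | 0.2 |
| 1.5 | 3.0 | 2.0 | none |

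A patient without Gilbert's syndrome enters at no more than 1.2 x ULN and so cannot be above 2 x ULN at entry, whatever the ULN.

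**Step 2: what happens to rule 3?** Write it as T and (B or I), where T is the confirmed aminotransferase elevation, B is bilirubin above 2 x ULN and I is INR above 1.5. At entry T is false: 13d caps ALT/AST at 2 x ULN, while T needs more than 3 x ULN, or the greater of 3 x ULN and 2 x Baseline. The rule as a whole is therefore not met. If B is true at baseline and stays true, T and (B or I) equals T.

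**Step 3: which SAP rows share the problem?**

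| Analyte | Highest permitted at screening | Lowest fixed threshold in the SAP 3.7.4 list | Baseline condition in the row |
|---|---|---|---|
| ALT/AST | 2 x ULN | 3 x ULN | not needed at entry; the combined row has one |
| ALP | 1.5 x ULN | 2 x ULN | yes |
| Total bilirubin (Gilbert's) | 3 mg/dL | 2 x ULN | none |

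When the ULN is below 1.5 mg/dL, bilirubin is the only analyte that eligibility admits above the table's own threshold, and its row has no baseline condition.

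**Step 4: size.** Each active arm has 25 x 4/5 = 20 patients, and pooled placebo has 4 x 5 = 20. One misattributed patient is 1/20 = 5% of an arm, or 1/80 = 1.25% of the pooled active group. The documents give no count of Gilbert's patients, and none can be derived from them.

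**The case against.** The strongest reply is that the report as a whole is not blind to baseline. SAP 3.7.4 plans a total bilirubin shift table on original and confirmed values, by-visit change from baseline for the chemistry panel (including direct and indirect bilirubin), listings of all laboratory results, and a dedicated listing of liver tests for every patient with a confirmed 3-fold ALT/AST elevation. Gilbert's patients can also be randomised to placebo, so no direction of bias is evident. This stands as mitigation. It does not correct the two rows: a reader of either would have to go to the listings to learn that a counted patient began above the threshold.

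A second reply is that an entry limit and an on-treatment stopping rule serve different purposes, and the sponsor may want the cautious rule for everyone. That may be so, but the protocol does not say it.

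Four stronger readings are tempting and are not supported:

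- *That a patient can meet stopping rule 3 before the first dose.* Only the bilirubin part can be true then (Step 2). The SAP rows count post-baseline values only, so a pre-dose value is not itself counted.
- *That the bilirubin alert at above ULN (section 8.5.1) is also an error because it lies below the entry limits.* That section says the alert levels are set to anticipate a combined elevation. The ALP alert is likewise below its entry limit. An alert prompts review; it does not stop treatment.
- *That dose selection would be distorted.* Section 10.1.4 names treatment-related SAEs and platelet reductions. Liver findings could enter only through its general reference to other safety considerations.
- *That Phase 1 makes the joint event likely.* Section 2.3.4 reports treatment-related ALT above 3 x ULN in 2 subjects of the 60 mg every-4-week cohort, but both had a history of ALT elevation. This shows that the aminotransferase part can occur, and no more.

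**Conclusion.** The inconsistency is real and narrow. If the laboratory ULN is below 1.5 mg/dL, criterion 13e permits entry above the bilirubin limit of rule 3 and of SAP 3.7.4, and neither makes allowance for baseline bilirubin. For such a patient the joint rule rests on aminotransferases alone, and an unchanged bilirubin is tabulated as a post-baseline abnormality.

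This rests on an assumed ULN and on at least one enrolled Gilbert's patient with bilirubin above 2 x ULN. The stopping consequence further needs a confirmed aminotransferase rise in that same patient. The affected number may be zero. The textual mismatch is certain and its practical effect is not. The correction is worth making because it is nearly free and concerns a named safety endpoint.

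**What to change.** **SAP 3.7.4.** Keep the unqualified total bilirubin row. Add a companion row, or split it by baseline status: baseline at or below 2 x ULN or missing, versus baseline above 2 x ULN, with baseline as defined in SAP 3.2.4. Simply copying the ALP condition would be worse, because it would remove from the row a patient who truly worsened from, say, 2.1 to 6 x ULN. In the combined ALT/AST-plus-bilirubin row, footnote patients with documented Gilbert's syndrome and give their baseline total bilirubin and their direct bilirubin, which is already in the chemistry panel. The split alone cannot identify a Gilbert's patient who drifts from just below to just above 2 x ULN; extending the footnote to the bilirubin row would.

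**Protocol.** Reconcile criterion 13e with the bilirubin part of section 8.6.1 criterion 3, and state whether that criterion is meant to apply unchanged to patients admitted under the Gilbert's exception. Which clinical threshold applies is for the sponsor.

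**Cost.** One extra table row, one footnote and a short protocol clarification. No new data are needed.

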6. STUDY PROCEDURES

6.1 Study Schedule

All required study procedures are outlined in [Appendices A, B, and C](#).

6.1.1 Screening

Written informed consent for the study will be obtained prior to the performance of any study-related procedures including screening procedures. An up to 4-week period is provided for completing screening assessments and determining patient eligibility for the study. Abnormal screening results may be re-tested once for determination of patient eligibility after consultation with the Sponsor Medical Monitor. Patients may be re-screened 1 time in order to determine eligibility.

During the screening period, patients will undergo a medical history and physical examination including vital signs, 12-lead electrocardiogram (ECG) and have blood and urine samples taken for clinical laboratory testing. Patients will be screened for HIV, hepatitis B, and hepatitis C.

As part of the screening period, patients not already on a stable diet will have 2 weeks of diet run-in, followed by a qualification visit, during which final eligibility assessments will be performed. Patients on a stable diet, known to the investigator and followed at the site, may go from Screening to qualification without a 2-week diet run-in. At the qualification visit TGs will be measured.

6.1.2 Treatment Period

Treatment period is defined as the time between the first and the last doses of study drug plus one dosing interval. During the treatment period, patients will report to the study center for clinic visits. Patients will receive 10 mg doses of Study Drug administered by SC injection once every 4 weeks for up to 49 weeks in Cohort A, 50 mg doses of Study Drug administered by SC injection once every 4 weeks for up to 49 weeks in Cohort B, 15 mg doses of Study Drug administered by SC injection once every 2 weeks for up to 51 weeks in Cohort C, or 10 mg doses of Study Drug administered by SC injection once per week (weekly) for up to 52 weeks in Cohort D ([Section 8.1](#)).

Collection and measurement of vital signs, physical examination results, ECGs, clinical laboratory parameters ([Appendix B](#)), ISIS 678354 plasma concentrations, immunogenicity and biomarker samples, AEs and concomitant medication/procedure information will be performed according to the Schedule of Procedures in [Appendix A](#).

Extensive Pharmacokinetic (PK) Subgroup Only:

Within each cohort, a subgroup of approximately 10 patients, who will consent to extensive PK sampling, will undergo additional PK sampling, in what is referred to as the PK Subgroup in this study. Patients in this subgroup will have additional PK sampling time points in order to evaluate the plasma PK parameters of ISIS 678354. Patients in this subgroup will have additional visits to the clinic during the treatment period in order to collect blood samples for PK assessment ([Appendix C](#)).

6.1.3 Post-Treatment Period

Each patient will be followed for safety assessments for 13 weeks post end of treatment period. During the post-treatment follow-up period, patients will return to the Study Center for 3 outpatient visits as outlined in [Appendix A](#) for safety and clinical laboratory evaluations and for blood sampling for PK ([Appendices A](#) and [C](#)).

6.2 Additional Study Assessments

6.2.1 Laboratory Assessments

Laboratory analyte samples will be collected throughout the study as per the Schedule of Procedures in [Appendix A](#). A list of these analytes is contained in [Appendix B](#).

Routine blood chemistry and urine samples should be taken after fasting for at least 10 hours and preferably not more than 12 hours. Any confirmatory test, or test taken for safety reasons, may be taken at any time, irrespective of fasting status, but no later than 7 days after the initial result is obtained. During preparation for fasting samples, the patient can drink water and they should ensure that they consume sufficient water in order to not become dehydrated.

If tests are uninterpretable (e.g., due to clumping, hemolysis or quantity not sufficient) or missing, a repeat blood or urine specimen should be re-drawn as soon as possible (ideally within 1 week).

While on treatment, hematology samples will be collected every 14 days (± 2 days). Each time a hematology lab is drawn and sent to the central laboratory for analysis, an additional sample should be collected in parallel and analyzed locally. In the event that both the central and local samples are unreportable (e.g., due to hemolyzed or clumped blood samples), patient dosing cannot continue until another sample is repeated and determined not to have met a platelet stopping rule.

If there is no reportable platelet count within 14 days of the last platelet count, the Investigator will contact the patient to hold dosing until a new platelet count is obtained and reviewed.

While on treatment blood and urine samples for renal function testing will also be collected every 14 days (± 2 days) and sent to the central laboratory for analysis for the first 3 months of the study treatment, and monthly thereafter during the Treatment Period per [Section 8.5.2](#).

While on treatment liver function testing will also be collected every 14 days (± 2 days) and sent to the central laboratory for analysis for the first 3 months of the study treatment, and monthly thereafter during the Treatment Period per [Section 8.5.1](#).

All lab samples are to be sent to the central laboratory by overnight courier and processed. Lab Alerts issued as per protocol safety monitoring requirements or stopping rules will indicate the applicable protocol section to facilitate review and will be immediately and simultaneously sent by email to the Investigator, the Sponsor and the CRO Medical Monitors, the Sponsor Drug Safety Physician, and the Clinical Trial Manager (CTM), and should be received by them within 2 days from sample collection. Hematology results from the site's local laboratories are received by the study center staff per the local laboratories' standard reporting time, and should be entered as soon as possible into the eCRF to inform the Sponsor and CRO study monitoring teams.

All platelet count results must be reviewed promptly (within 48 hours of receipt) by the Investigator, or designee, to ensure that the count has not met the stopping rule and to determine whether the rate of decline is suggestive that the patient could be approaching the dose interruption rule of 75,000/mm³ as specified in [Section 8.6.3](#). Any case of a platelet count reduction to levels below 50,000/mm³ is considered an adverse event of special interest and must be reported in an expedited fashion to the Sponsor as per [Sections 9.3.3.1](#) and [9.4.1](#).

All liver and renal function tests must also be reviewed promptly (within 48 hours of receipt) by the Investigator, or designee, to ensure that the result has not met the stopping rule. Any event meeting renal stopping rules criteria described in [Section 8.6.2](#) is considered an adverse event of special interest and must be reported in an expedited fashion to the Sponsor as per [Sections 9.3.3.1](#) and [9.4.1](#).

All lab alerts received, including those related to platelet, liver, or renal function monitoring/stopping rules, are also reviewed promptly by the Sponsor and the CRO Medical Monitors who will agree on actions to be taken. Within 24 hours of receiving an actionable lab alert the CRO Medical Monitor will communicate instructions to the Investigator and the study personnel by emailing them the Safety Surveillance Form that needs to be completed and signed by the Investigator/study personnel and promptly returned to the Sponsor and CRO Medical Monitor. In urgent cases, such as platelets results below 50,000/mm³, or liver or renal test results reaching a critical stopping rule, the Investigator must also be contacted by phone.

Further information on safety monitoring and actions to be taken by the Study Investigator in the event of reduced platelet count are provided in [Sections 8.5.3](#) and [8.6.3](#).

